## Background

Carbonyl stress is the abnormal accumulation of carbonyl metabolites, such as methylglyoxal and acrolein, leading to increased modification of protein and DNA and contributing to cell and tissue dysfunction in aging and many chronic diseases. Dietary flavonoids have been reported to have the capacity to scavenging of these reactive carbonyl species in vitro and in mice. However, this effect has not been demonstrated in humans.

## Study Objectives

The goal of this study is to determine the formation and kinetics of reactive carbonyl adducts of dietary flavonoids (soymilk, blueberry and green tea) in humans after a single dose of the dietary flavonoids. We speculate that the dietary flavonoids (soymilk, blueberry and green tea) can react with endogenous reactive carbonyls species to form reactive carbonyl adducts in the body, eventually alleviating the damaging effects of reactive carbonyls species on human health. Study on the formation and kinetics of reactive carbonyl adducts of dietary flavonoids is also expected to be able to provide substantial evidence for the health effects of regular dietary flavonoids (soymilk, blueberry and green tea) consumption in epidemiological studies.

## Study Design

This study follows a **randomized, crossover design**, where participants will consume each intervention (soymilk, blueberry, and green tea) in separate study periods with a washout phase in between.

- **Study Duration:** 17 days
- **Number of Participants:** 16 healthy adults for each intervention
- **Intervention Groups:**
  - Dietary Flavonoids (Soymilk) Consumption and Placebo
  - Dietary Flavonoids (Blueberry) Consumption and Placebo
  - Dietary Flavonoids (Green Tea) Consumption and Placebo

## Study Methods- Participant Selection

Minimum Age: 25 Years

Maximum Age: 70 Years

Sex: All

Criteria:

Inclusion Criteria:

1. Age 25-70 years
2. BMI between 18 and 30
3. Have no known allergy to soy milk
4. Be not taking antibiotics for six months
5. Be not currently taking medication
  - a. No taking any prescription drugs
  - b. If supplements were taken, flavonoid-enriched supplements (see list below) should be avoided.

Major brands Notes: All flavonoid-enriched supplements should be avoided. Soy Isoflavones/ tea/blueberry Lipo-Flavonoid Citrus Bioflavonoids Complex Super Flavonoids Super Antioxidants Quercetin Supplement Essential-C and flavonoids Milk Thistle Other flavonoids supplements, including but not limited: Luteolin, Rutin, etc

- c. No any drugs or supplements within three weeks of the experiment
6. Be nonsmoking
7. Have no alcoholic intoxication

- a. No alcoholic addiction
- b. < 3-4 drinks per week (less than 2 glasses (300 mL) per drink)
- c. No alcohol within 3 weeks of the experiment
- 8. Have no extended exposure to industrial wastes

Exclusion Criteria:

- 1. Disease: gout, heart disease, peripheral vascular disease, degenerative kidney, degenerative liver, diabetes, GI disorders, or endocrine disorders
- 2. Cancer patients
  - a. Currently diagnosed cancer patients will be excluded;
  - b. Medication free for >2 years could be considered

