## Study Methods- Procedures

### 1. Dietary Flavonoids (Soymilk) Consumption and Placebo

#### Week 1 (Wash-in Period: Days 1-7)

Sixteen (16) healthy volunteers were recruited and instructed to avoid consuming soymilk, green tea, and blueberry products starting one week before the intervention and continuing throughout the entire three-week study period.

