#### Week 2 (First Intervention: Day 8)

Participants were randomized into two groups:

- **Soymilk-first group:** Consumed a breakfast including 460 mL of soymilk in a single dose.
- **Control-first group:** Consumed a breakfast including 460 mL of milk in a single dose.

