#### Week 3 (Cross-over: Day 15)

Participants switched interventions:

- Those who previously consumed soymilk in Week 2 now consumed milk.
- Those who previously consumed milk in Week 2 now consumed soymilk.

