### Week 2 (First Intervention: Day 8)

Participants were randomized into two groups:

- **Blueberry-first group:** Consumed a breakfast including 460 mL of blueberry water in a single dose.
- **Control-first group:** Consumed a breakfast including 460 mL of placebo sweet water in a single dose.

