### Week 3 (Cross-over: Day 15)

Participants switched interventions:

- Those who previously consumed blueberry water in Week 2 now consumed placebo sweet water.
- Those who previously consumed placebo sweet water in Week 2 now consumed blueberry water.

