### Week 2 (First Intervention: Day 8)

Participants were randomized into two groups:

- **Green tea-first group:** Consumed a breakfast including 460 mL of green tea in a single dose.

- **Control-first group:** Consumed a breakfast including 460 mL of water in a single dose.

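### The only allergy criterion names soy milk, although the soymilk sub-study also serves milk and the other two sub-studies serve blueberry water and green tea (minor safety gap in the written criteria)

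*Combined protocol and SAP*

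**What the plan says.** One eligibility list, under Study Methods- Participant Selection, serves all three sub-studies. Its only allergy item is inclusion criterion 3: "Have no known allergy to soy milk". The first exclusion criterion reads "Disease: gout, heart disease, peripheral vascular disease, degenerative kidney, degenerative liver, diabetes, GI disorders, or endocrine disorders", and the second concerns cancer. Neither mentions allergy, milk or lactose. Blueberry and tea appear in this section only among the supplements to avoid.

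The procedures then set out what is served:

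- **Soymilk sub-study.** On Day 8 the control-first group "Consumed a breakfast including 460 mL of milk in a single dose". On Day 15 the groups switch: "Those who previously consumed soymilk in Week 2 now consumed milk".
- **Blueberry sub-study.** On Day 8 the blueberry-first group "Consumed a breakfast including 460 mL of blueberry water in a single dose". On Day 15, "Those who previously consumed placebo sweet water in Week 2 now consumed blueberry water".
- **Green tea sub-study.** On Day 8 the tea-first group "Consumed a breakfast including 460 mL of green tea in a single dose". The group that had water first receives the tea on Day 15.

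**The concern.** The protocol already accepts the principle that a known allergy to a served product should bar entry, because it applies that rule to soy milk. It does not carry the rule to the drink that the same people receive in the other period, or to the active drinks of the other two sub-studies. The list reads as if it had been written around one product and not extended when the comparator and the further sub-studies were added.

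What is at stake is participant safety under the written rule. A volunteer with a known milk allergy can meet every listed criterion, enter the soymilk sub-study and be allocated a full serving of milk. The same holds for a known allergy to blueberry or green tea in the sub-study that serves it. No estimate, error rate or sample size depends on this.

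**Working it through.** The plan gives no figure to reproduce here. The check sets the eligibility text against the procedures, with one count.

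**Step 1. What the allergy criterion covers, by sub-study.**

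| Sub-study | Active drink | Named in criterion 3? | Comparator | Named in criterion 3? |
|---|---|---|---|---|
| Soymilk | soymilk | yes | milk | no |
| Blueberry | blueberry water | no | placebo sweet water | no (ingredients not given) |
| Green tea | green tea | no | water | not relevant |

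Three products that could matter are therefore unnamed: milk, blueberry and green tea. The composition of the blueberry water is not given either. I assume only that it contains blueberry.

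**Step 2. Whether another listed criterion closes the gap.** The disease exclusion includes GI disorders. That might remove some people with milk intolerance, but a food allergy is not ordinarily classed as a GI disorder. The medication, supplement, smoking, alcohol and industrial-exposure items do not bear on food allergy.

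**Step 3. How many people the milk comparator reaches.** Sixteen volunteers are recruited to the soymilk sub-study. Let *a* be the number in the control-first group, so that 16 − *a* are in the soymilk-first group.

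- Milk on Day 8: *a*
- Milk on Day 15: 16 − *a*
- Total: *a* + (16 − *a*) = 16

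The total does not depend on the split between sequences. It does assume that everyone completes both periods. A soymilk-first participant who withdraws before Day 15 never receives milk.

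**Step 4. Size of a records check, if one is needed.** Study Design can be read as the same people taking all three interventions, while the procedures recruit 16 volunteers for each. With the same participants throughout, the check covers 16 people. With separate cohorts it covers 3 × 16 = 48. The milk check covers 16 under either reading.

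**The case against.** The strongest case on the other side is that the places where a fuller screen would naturally sit cannot be seen. Scheme 1 covers recruitment, screening and enrolment, but its content is missing from the text available, and the consent pages were removed. Either may ask about milk, blueberry and tea. The route to harm is also narrow: an adult who knows of the allergy would have to accept a full serving of that food at breakfast. And the sub-study procedures describe recruitment and dosing in the past tense, so an amendment may come too late to matter.

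All of this limits the point without removing it. The criteria list itself is visible, and it is narrower than the products served. The protocol did not rely on volunteers to speak up about soy milk, so it has no evident reason to rely on that for milk. The status of the trial is unclear, since Study Design and the Statistical Analysis Plan use the future tense. The fix below allows for both cases.

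Four stronger readings are tempting, and the documents support none of them:

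- *That a person with an allergy was, or would be, dosed.* Nothing in the documents indicates this, and they give no allergy frequency from which to derive a rate.
- *That milk stands out because it is missing from the wash-in instruction.* Volunteers are "instructed to avoid consuming soymilk, green tea, and blueberry products starting one week before the intervention". That is a dietary restriction on the three flavonoid sources under test, not an allergy screen. A product's presence or absence there says nothing about safety.
- *That all 16 soymilk-study participants necessarily receive milk.* This holds only for those who complete both periods.
- *That the rest of the study breakfast is a further gap.* The breakfast is not described beyond the drink, so no gap can be shown there.

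**Conclusion.** The point holds as a minor safety gap in the written eligibility criteria, worth considering but no more. The one allergy item covers soy milk and leaves out the milk comparator in the same sub-study, as well as blueberry and green tea in the others. For milk, up to 16 people are served the unlisted product, and exactly 16 if all complete both periods. That is a count of people served, not a measure of risk.

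The conclusion rests on the criteria list as printed and is subject to whatever Scheme 1 and the consent pages contain. It has no bearing on the primary objective, the repeated-measures analysis or the power statement.

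**What to change.** Reword inclusion criterion 3 along these lines: *no known allergy to any study or comparator product the participant will receive (soymilk, milk, blueberry, green tea)*. Put the same item on the screening form. If Scheme 1 or the form already asks this, bring that wording into the criteria list so that the two agree.

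If dosing is complete, confirm from the screening records that no one with such an allergy was dosed. Start with milk in the soymilk sub-study, where the criterion covers one of the two drinks and omits the other.

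While the trial is enrolling, the cost is a one-line amendment, the matching line on the form, and possibly a few more screen failures. After completion, it is a short records check of 16 to 48 people. Nothing in the design or analysis changes.

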## Study Methods- Procedures

### 1. Dietary Flavonoids (Soymilk) Consumption and Placebo

#### Week 1 (Wash-in Period: Days 1-7)

Sixteen (16) healthy volunteers were recruited and instructed to avoid consuming soymilk, green tea, and blueberry products starting one week before the intervention and continuing throughout the entire three-week study period.

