#### Biological sample collection:

- Urine and blood samples were collected at multiple time points over a 24-hour period.
- Fecal samples were collected at different time points over a 48-hour period.

Participants continued to avoid consuming soymilk, green tea, and blueberry products.

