#### Biological sample collection:

- Urine and blood samples were collected at multiple time points over a 24-hour period.
- Fecal samples were collected at different time points over a 48-hour period.

Participants continued to avoid consuming soymilk, green tea, and blueberry products until Day 17.

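### Foods are restricted only as three named products while supplements are barred as a class, so other dietary sources of the measured flavonoids may be eaten during wash-in and sampling

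*Combined protocol and SAP*

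**What the plan says.** **Foods.** Under Week 1 (Wash-in Period) of each sub-study, volunteers are "instructed to avoid consuming soymilk, green tea, and blueberry products starting one week before the intervention". After the first intervention the wording is "Participants continued to avoid consuming soymilk, green tea, and blueberry products", and after the cross-over it is "Participants continued to avoid consuming soymilk, green tea, and blueberry products until Day 17". The three items are the same in the soymilk, blueberry and green tea studies.

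**Supplements.** Participant Selection, inclusion item 5b, is set by content: "All flavonoid-enriched supplements should be avoided". Its list names soy isoflavones and tea in general, and ends open: "Other flavonoids supplements, including but not limited: Luteolin, Rutin, etc". Item 5c goes further and drops the content condition: "No any drugs or supplements within three weeks of the experiment".

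**Other dietary control.** The only other restriction on intake is on alcohol, with a limit on usual drinking and "No alcohol within 3 weeks of the experiment". On the dosing day the text describes a test breakfast (for example, "Consumed a breakfast including 460 mL of soymilk in a single dose") without its remaining composition, and no standard meals afterwards.

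**Sampling.** In each period blood and urine are collected over 24 hours and feces over 48 hours. The Scheme 2 calendar adds a 0 h fecal sample before each period.

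**The concern.** The supplement rules show that the plan regards flavonoids from outside the test drink as interference. The food rule does not follow the same logic. A soy isoflavone capsule is barred, but a soy food other than soymilk is not; a tea supplement is barred, but a tea other than green tea is not.

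This matters because of what the study sets out to show. The Study Objectives concern the formation and kinetics of adducts after one dose, and the Statistical Analysis Plan makes detection of adducts the primary objective. Both readings are cleanest when the test drink is the only relevant source during the collection window. A participant who follows the stated rule exactly can still take in the measured flavonoids from another food several times within that window, on either day.

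**Working it through.** **1. The two rules side by side**

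| | Supplements (items 5b, 5c) | Foods (Procedures, all sub-studies) |
|---|---|---|
| Defined by | Flavonoid class; then all supplements within three weeks | Three named products |
| Other soy, tea or berry sources | Barred | Not mentioned |
| In force during 24 h and 48 h collection | Yes, if 5c covers the study itself | Yes, for the three products only |

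No readable section contains a low-flavonoid diet, a standard meal after breakfast, or a diet record.

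**2. What the crossover protects.** Let a participant's amount be A + B1 on the active day and B2 on the control day, where A comes from the test drink and B1, B2 from other food. If background intake adds to the signal and does not depend on which drink was given, B1 and B2 have the same mean and the expected difference is A. Three things are not protected: the variance of B1 − B2, the presence of B2 on the control day, and the part of B1 eaten after dosing, which enters the late active-day samples.

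**3. The plan's own power figure.** The Statistical Analysis Plan gives n=16, 80% power and effect size 0.809, without alpha, sidedness or a definition of the effect size. At two-sided 0.05, noncentral-t power is 85.6% for a paired test with 16 people and 60.0% for two independent groups of 16. Neither equals 80%, although some unstated settings come close (for example, 14 people analysed in a paired test have a detectable effect of 0.810). The figure is therefore not shown to be wrong. The paired setting used next is an assumption.

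**4. Added noise (illustration).** Suppose background diet adds a fraction v to the variance of the paired difference. Then d = 0.809/√(1+v), noncentrality = d√16, df = 15, critical t = 2.131.

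| v | d | d√16 | Power |
|---|---|---|---|
| 0 | 0.809 | 3.236 | 85.6% |
| 10% | 0.771 | 3.085 | 82.2% |
| 25% | 0.724 | 2.894 | 77.2% |
| 50% | 0.661 | 2.642 | 69.5% |

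The values of v are assumed.

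**5. Detection (illustration).** Let f be the share who form a detectable adduct from the test food (assumed 70% to 80%) and q the share positive from other food on any one day. The active-day rate is 1 − (1−f)(1−q), so the active-minus-control difference in detection is f(1−q). With f = 70% and q = 25% it is 0.70 × 0.75 = 52.5 points instead of 70. Power of an exact McNemar test, n=16, two-sided 0.05, for f = 70% and 80%:

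| q | Background independent between days | Same people positive on both days |
|---|---|---|
| 0 | 99.8% / 100% | 99.8% / 100% |
| 5% | 97.7% / 99.7% | 99.6% / 100% |
| 10% | 93.8% / 98.6% | 99.0% / 99.9% |
| 25% | 75.6% / 89.3% | 92.7% / 98.1% |

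A material loss appears only when q is high and a person's two days are unrelated. The plan specifies repeated-measures ANOVA and not this test, so the table shows sensitivity only.

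**The case against.** The strongest case against has five parts.

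- *The two rules do not contradict each other.* One is an eligibility criterion and the other a procedure, and they may differ in breadth. This stands. The point is a gap in the food rule, not an inconsistency.
- *Harm is not shown.* A reader might infer that the kinetics and control-day results are contaminated. The documents do not support that: they give no background intake, adduct level or assay limit. That other foods carry the measured flavonoids is general knowledge, although item 5b shows that the plan recognises other sources. Only *can* is justified.
- *The design already limits bias.* Order is randomised, each person has a control day, and a 0 h fecal sample precedes each period. This stands for the average contrast in amount. It does not cover intake after dosing.
- *A large loss of power might be inferred from the 25% detection scenario.* That needs a high background rate and no correlation between a person's two days. Diet is plausibly habitual, and at 10% or less power stays near 94% or higher.
- *A fuller food list may exist.* Consent pages and some figures are not available, so this is possible. If such a list exists, citing it in the protocol settles the matter.

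**Conclusion.** The point holds as a low-cost improvement. Followed exactly, the stated food rule allows other sources of the measured flavonoids during wash-in and both collection windows. The consequences are possible noise, control-day signal and distorted late active-day samples. The average active-minus-control difference in amount is not biased, provided that background intake is additive and unrelated to the drink given.

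The size cannot be determined from the documents. The fall in power from 86% to between 82% and 70% rests on an assumed paired t-test at two-sided 0.05 and an assumed 10% to 50% addition to the variance. It is not an estimate for this trial and does not show that the plan's 80% is wrong.

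**What to change.** In each sub-study, define food avoidance by the flavonoids being measured: other soy foods in the soymilk study, other teas in the green tea study, other anthocyanin-type berries in the blueberry study. Apply it at least through wash-in and both collection windows. The cost is a longer instruction sheet and some dietary burden.

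The Procedures are written in the past tense, so collection may be complete. In that case:

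- Use the control-day value at each time point as the comparator, with the 0 h value as baseline where one was taken.
- Report the control-day detection rate for all participants.
- Do not exclude participants because an adduct was detected on the control day. That selects on the outcome: it removes the people who count against an active-control difference and inflates the contrast.
- Note that a positive 0 h sample in the second period may be carry-over from an active first period and need not reflect diet.

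This version costs only some added analysis and reporting.

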#### Week 2 (First Intervention: Day 8)

Participants were randomized into two groups:

- **Soymilk-first group:** Consumed a breakfast including 460 mL of soymilk in a single dose.
- **Control-first group:** Consumed a breakfast including 460 mL of milk in a single dose.

#### Biological sample collection:

- Urine and blood samples were collected at multiple time points over a 24-hour period.
- Fecal samples were collected at different time points over a 48-hour period.

Participants continued to avoid consuming soymilk, green tea, and blueberry products.

#### Week 3 (Cross-over: Day 15)

Participants switched interventions:

- Those who previously consumed soymilk in Week 2 now consumed milk.
- Those who previously consumed milk in Week 2 now consumed soymilk.

#### Biological sample collection:

- Urine and blood samples were collected at multiple time points over a 24-hour period.
- Fecal samples were collected at different time points over a 48-hour period.

Participants continued to avoid consuming soymilk, green tea, and blueberry products until Day 17.

## 2. Dietary Flavonoids (Blueberry) Consumption and Placebo

### Week 1 (Wash-in Period: Days 1–7)

Sixteen (16) healthy volunteers were recruited and instructed to avoid consuming soymilk, green tea, and blueberry products starting one week before the intervention and continuing throughout the entire three-week study period.

### Week 2 (First Intervention: Day 8)

Participants were randomized into two groups:

- **Blueberry-first group:** Consumed a breakfast including 460 mL of blueberry water in a single dose.
- **Control-first group:** Consumed a breakfast including 460 mL of placebo sweet water in a single dose.

#### Biological sample collection:

- Urine and blood samples were collected at multiple time points over a 24-hour period.
- Fecal samples were collected at different time points over a 48-hour period.

Participants continued to avoid consuming soymilk, green tea, and blueberry products.

